### 10.9.7. Efficacy Figures

Efficacy: Figures					
No.	Population	IDSL / Example Shell	Title	Programming Notes	Deliverable [Priority]
Primary Efficacy Endpoint					
2.1.	ITT	Study Specific	Box Plot of Change from Baseline in Clinic Trough FEV 1 (L) at Week 4, Week 12 and Week 24 (On- and Post-Treatment)	On- and post-treatment data	SAC
2.2.	ITT	Study Specific	Empirical Distribution Function Plot of Change from Baseline in Clinic Trough FEV 1 (L) at Week 4, Week 12 and Week 24 (On- and Post-Treatment)	On- and post-treatment data	SAC
2.3.	ITT	Study Specific	Least Squares Mean (95% CI) Change from Baseline in Clinic Trough FEV 1 (L) up to Week 24 (On- and Post-Treatment)	On- and post-treatment data	SAC
2.4.	ITT	Study Specific	Least Squares Mean (95% CI) Treatment Difference in Change from Baseline in Clinic Trough FEV 1 (L) up to Week 24 (On- and Post-Treatment)	On- and post-treatment data	SAC
2.5.	ITT	Study Specific	Box Plot of Change from Baseline in Clinic Trough FEV 1 (L) at Week 4, Week 12 and Week 24 (On-Treatment)	On-treatment data only	SAC
2.6.	ITT	Study Specific	Empirical Distribution Function Plot of Change from Baseline in Clinic Trough FEV 1 (L) at Week 4, Week 12 and Week 24 (On-Treatment)	On-treatment data only	SAC
2.7.	ITT	Study Specific	Least Squares Mean (95% CI) Change from Baseline in Clinic Trough FEV 1 (L) up to Week 24 (On-Treatment)	On-treatment data only	SAC
2.8.	ITT	Study Specific	Least Squares Mean (95% CI) Treatment Difference in Change from Baseline in Clinic Trough FEV 1 (L) up to Week 24 (On-Treatment)	On-treatment data only	SAC
2.9.	ITT	Study Specific	Forest Plot of Least Squares Mean (95% CI) Treatment Difference in Change from Baseline in Trough FEV 1 (L) and Associated Supportive/Sensitivity Analyses at Week 24		SAC

Efficacy: Figures					
No.	Population	IDSL / Example Shell	Title	Programming Notes	Deliverable [Priority]
2.10.	ITT	Study Specific	Tipping Point Heat Plot for Mean Change from Baseline in Clinic Trough FEV 1 (L) Difference UMEC 62.5mcg – Placebo (On- and Post-Treatment)		SAC
2.11.	ITT	Study Specific	Tipping Point Line Plot for Mean Change from Baseline in Clinic Trough FEV 1 (L) Difference UMEC 62.5mcg – Placebo (On- and Post-Treatment)		SAC
2.12.	ITT	Study Specific	Tipping Point Heat Plot for Mean Change from Baseline in Clinic Trough FEV 1 (L) Difference UMEC 31.25mcg – Placebo (On- and Post-Treatment)		SAC
2.13.	ITT	Study Specific	Tipping Point Line Plot for Mean Change from Baseline in Clinic Trough FEV 1 (L) Difference UMEC 31.25mcg – Placebo (On- and Post-Treatment)		SAC
Secondary Efficacy Endpoint					
2.14.	ITT	Study Specific	Box Plot of Change from Baseline in Clinic FEV 1 (L) at 3 Hours post Dose at Week 24 (On-Treatment)	On-treatment data only	SAC
2.15.	ITT	Study Specific	Empirical Distribution Function Plot of Change from Baseline in Clinic FEV 1 (L) at 3 Hours post Dose at Week 24 (On-Treatment)	On-treatment data only	SAC
2.16.	ITT	Study Specific	Least Squares Mean (95% CI) Change from Baseline in Clinic FEV 1 (L) at 3 Hours post Dose at Week 24 (On-Treatment)	On-treatment data only	SAC
2.17.	ITT	Study Specific	Least Squares Mean (95% CI) Treatment Difference in Change from Baseline in Clinic FEV 1 (L) at 3 Hours post Dose at Week 24 (On-Treatment)	On-treatment data only	SAC
Other Efficacy Endpoints					
2.18.	ITT	Study Specific	Least Squares Mean (95% CI) Change from Baseline in Home AM PEF (L/min) over the 24-week Treatment Period by 4-Weekly Intervals (On- and Post-Treatment)	On- and post-treatment data	SAC

Efficacy: Figures					
No.	Population	IDS / Example Shell	Title	Programming Notes	Deliverable [Priority]
2.19.	ITT	Study Specific	Least Squares Mean (95% CI) Treatment Difference in Change from Baseline in Home AM PEF (L/min) over the 24-week Treatment Period by 4-Weekly Intervals (On- and Post-Treatment)	On- and post-treatment data	SAC
2.20.	ITT	Study Specific	Least Squares Mean (95% CI) Change from Baseline in Home AM PEF (L/min) over Weeks 1-24 (On- and Post-Treatment)	On- and post-treatment data	SAC
2.21.	ITT	Study Specific	Least Squares Mean (95% CI) Treatment Difference in Change from Baseline in AM PEF (L/min) over Weeks 1-24 (On- and Post-Treatment)	On- and post-treatment data	SAC
2.22.	ITT	Study Specific	Descriptive Weekly Mean Change from Baseline in Home AM PEF (L/min) from Weeks 1-24 (On- and Post-Treatment)	On- and post-treatment data	SAC
2.23.	ITT	Study Specific	Least Squares Mean (95% CI) Change from Baseline in Home PM PEF (L/min) over the 24-week Treatment Period by 4-Weekly Intervals (On- and Post-Treatment)	On- and post-treatment data	SAC
2.24.	ITT	Study Specific	Least Squares Mean (95% CI) Treatment Difference in Change from Baseline in Home PM PEF (L/min) over the 24-week Treatment Period by 4-Weekly Intervals (On- and Post-Treatment)	On- and post-treatment data	SAC
2.25.	ITT	Study Specific	Least Squares Mean (95% CI) Change from Baseline in Home PM PEF (L/min) over Weeks 1-24 (On- and Post-Treatment)	On- and post-treatment data	SAC
2.26.	ITT	Study Specific	Least Squares Mean (95% CI) Treatment Difference in Change from Baseline in Home PM PEF (L/min) over Weeks 1-24 (On- and Post-Treatment)	On- and post-treatment data	SAC
2.27.	ITT	Study Specific	Descriptive Weekly Mean Change from Baseline in Home PM PEF (L/min) from Weeks 1-24 (On- and Post-Treatment)	On- and post-treatment data	SAC

Efficacy: Figures					
No.	Population	IDS / Example Shell	Title	Programming Notes	Deliverable [Priority]
2.28.	ITT	Study Specific	Least Squares Mean (95% CI) Change from Baseline in Home Trough FEV1 (L) over the 24-week Treatment Period by 4-Weekly Intervals (On- and Post-Treatment)	On- and post-treatment data	SAC
2.29.	ITT	Study Specific	Least Squares Mean (95% CI) Treatment Difference in Change from Baseline in Home Trough FEV1 (L) over the 24-week Treatment Period by 4-Weekly Intervals (On- and Post-Treatment)	On- and post-treatment data	SAC
2.30.	ITT	Study Specific	Least Squares Mean (95% CI) Change from Baseline in Home Trough FEV1 (L) over Weeks 1-24 (On- and Post-Treatment)	On- and post-treatment data	SAC
2.31.	ITT	Study Specific	Least Squares Mean (95% CI) Treatment Difference in Change from Baseline in Home Trough FEV1 (L) over Weeks 1-24 (On- and Post-Treatment)	On- and post-treatment data	SAC
2.32.	ITT	Study Specific	Least Squares Mean (95% CI) Change from Baseline in Home Trough FEV1 (L) up to Week 8 by 1-Week Intervals (On- and Post-Treatment)	On- and post-treatment data	SAC
2.33.	ITT	Study Specific	Least Squares Mean (95% CI) Treatment Difference in Change from Baseline in Home Trough FEV1 (L) over Weeks 1-8 by 1-Week Intervals (On- and Post-Treatment)	On- and post-treatment data	SAC
2.34.	ITT	Study Specific	Descriptive Weekly Mean Change from Baseline in Home Trough FEV1 (L) from Weeks 1-24 (On- and Post-Treatment)	On- and post-treatment data	SAC
2.35.	ITT	Study Specific	Least Squares Mean (95% CI) Change from Baseline in Home PM FEV1 (L) over the 24-week Treatment Period by 4-Weekly Intervals (On- and Post-Treatment)	On- and post-treatment data	SAC
2.36.	ITT	Study Specific	Least Squares Mean (95% CI) Treatment Difference in Change from Baseline in Home PM FEV1 (L) over the 24-week Treatment Period by 4-Weekly Intervals (On- and Post-Treatment)	On- and post-treatment data	SAC

Efficacy: Figures					
No.	Population	IDSL / Example Shell	Title	Programming Notes	Deliverable [Priority]
2.37.	ITT	Study Specific	Least Squares Mean (95% CI) Change from Baseline in Home PM FEV1 (L) over weeks 1-24 (On- and Post-Treatment)	On- and post-treatment data	SAC
2.38.	ITT	Study Specific	Least Squares Mean (95% CI) Treatment Difference in Change from Baseline in Home PM FEV1 (L) over weeks 1-24 (On- and Post-Treatment)	On- and post-treatment data	SAC
2.39.	ITT	Study Specific	Least Squares Mean (95% CI) Change from Baseline in Daily Rescue Medication Use (puffs/day) over the 24-week Treatment Period by 4-Weekly Intervals (On- and Post-Treatment)	On- and post-treatment data	SAC
2.40.	ITT	Study Specific	Least Squares Mean (95% CI) Treatment Difference in Change from Baseline in Daily Rescue Medication Use (puffs/day) over the 24-week Treatment Period by 4-Weekly Intervals (On- and Post-Treatment)	On- and post-treatment data	SAC
2.41.	ITT	Study Specific	Least Squares Mean (95% CI) Change from Baseline in Daily Rescue Medication Use (puffs/day) over weeks 1-24 (On- and Post-Treatment)	On- and post-treatment data	SAC
2.42.	ITT	Study Specific	Least Squares Mean (95% CI) Treatment Difference in Change from Baseline in Daily Rescue Medication Use (puffs/day) over weeks 1-24 (On- and Post-Treatment)	On- and post-treatment data	SAC
2.43.	ITT	Study Specific	Empirical Distribution Function Plot of Change from Baseline in SGRQ Total Score at Week 4, Week 12 and Week 24 (On- and Post-Treatment)	On- and post-treatment data	SAC
2.44.	ITT	Study Specific	Least Squares Mean (95% CI) Change from Baseline in SGRQ Total Score at Week 4, Week 12 and Week 24 (On- and Post-Treatment)	On- and post-treatment data	SAC
2.45.	ITT	Study Specific	Least Squares Mean (95% CI) Treatment Difference in Change from Baseline in SGRQ Total Score at Week 4, Week 12 and Week 24 (On- and Post-Treatment)	On- and post-treatment data	SAC

Efficacy: Figures					
No.	Population	IDS / Example Shell	Title	Programming Notes	Deliverable [Priority]
2.46.	ITT	Study Specific	Bar Chart of Percent of Subjects Meeting a Responder Threshold of $\geq 4$ Points Improvement (Decrease) from Baseline for the SGRQ Total Score at Week 24 (On- and Post-Treatment)	On- and post-treatment data	SAC
2.47.	ITT	Study Specific	Forest plot of Least Squares Mean (95% CI) Treatment Difference in Change from Baseline in SGRQ total score and SGRQ Domain Scores at Week 24	On- and post-treatment data	SAC
2.48.	ITT	Study Specific	Least Squares Mean (95% CI) Change from Baseline in AQLQ Total Score at Week 4, Week 12 and Week 24 (On- and Post-Treatment)	On- and post-treatment data	SAC
2.49.	ITT	Study Specific	Least Squares Mean (95% CI) Treatment Difference in Change from Baseline in AQLQ Total Score at Week 4, Week 12 and Week 24 (On- and Post-Treatment)	On- and post-treatment data	SAC
2.50.	ITT	Study Specific	Bar Chart of Percent of Subjects Meeting a Responder Threshold of $\geq 0.5$ Points Improvement (Increase) from Baseline for the AQLQ Total Score at Week 24 (On- and Post-Treatment)	On- and post-treatment data	SAC
2.51.	ITT	Study Specific	Empirical Distribution Function Plot of Change from Baseline in E-RS Total Score over the 24 weeks Treatment Period by 4-Weekly Intervals (On- and Post-Treatment)	On- and post-treatment data	SAC
2.52.	ITT	Study Specific	Least Squares Mean (95% CI) Change from Baseline in E-RS Total Score over the 24 weeks Treatment Period by 4-Weekly Intervals (On- and Post-Treatment)	On- and post-treatment data	SAC
2.53.	ITT	Study Specific	Least Squares Mean (95% CI) Treatment Difference in Change from Baseline in E-RS Total Score over the 24 weeks Treatment Period by 4-Weekly Intervals (On- and Post-Treatment)	On- and post-treatment data	SAC
2.54.	ITT	Study Specific	Least Squares Mean (95% CI) Change from Baseline in E-RS Total Score over Weeks 1-24 (On- and Post-Treatment)	On- and post-treatment data	SAC

Efficacy: Figures					
No.	Population	IDSL / Example Shell	Title	Programming Notes	Deliverable [Priority]
2.55.	ITT	Study Specific	Least Squares Mean (95% CI) Treatment Difference in Change from Baseline in E-RS Total Score over Weeks 1-24 (On- and Post-Treatment)	On- and post-treatment data	SAC
2.56.	ITT	Study Specific	Empirical Distribution Function Plot of Change from Baseline in ACQ-5 Total Score at Week 4, Week 12 and Week 24 (On- and Post-Treatment)	On- and post-treatment data	SAC
2.57.	ITT	Study Specific	Least Squares Mean (95% CI) Change from Baseline in ACQ-5 Total Score at Week 4, Week 12 and Week 24 (On- and Post-Treatment)	On- and post-treatment data	SAC
2.58.	ITT	Study Specific	Least Squares Mean (95% CI) Treatment Difference in Change from Baseline in ACQ-5 Total Score at Week 4, Week 12 and Week 24 (On- and Post-Treatment)	On- and post-treatment data	SAC
2.59.	ITT	Study Specific	Bar Chart of Percent of Subjects Meeting a Responder Threshold of $\geq 0.5$ in Change (Decrease) from Baseline for the ACQ-5 Total Score at Week 24 (On- and Post-Treatment)	On- and post-treatment data	SAC
2.60.	ITT	Study Specific	Adjusted Moderate/Severe Asthma Exacerbations Rate Ratio (On- and Post-Treatment)	On- and post-treatment data	SAC
2.61.	ITT	Study Specific	Kaplan-Meier Plot of Time to First Moderate/Severe Asthma Exacerbation (On- and Post-Treatment)	On- and post-treatment data	SAC
2.62.	ITT	Study Specific	Adjusted Severe Asthma Exacerbations Rate Ratio (On- and Post-Treatment)	On- and post-treatment data	SAC
2.63.	ITT	Study Specific	Kaplan-Meier Plot of Time to First Severe Asthma Exacerbation (On- and Post-Treatment)	On- and post-treatment data	SAC

### 10.9.8. Safety Tables

Safety: Tables					
No.	Population	IDSL / Example Shell	Title	Programming Notes	Deliverable [Priority]
Treatment Exposure					
3.1.	ITT	EX1	Summary of Exposure to Open-Label FF100mcg During the Run-in Period		SAC
3.2.	ITT	EX1	Summary of Treatment Exposure	ICH E3	SAC
3.3.	ITT	Study Specific	Summary of Post-Treatment Duration on Study		SAC
Adverse Events (AEs)					
3.4.	ITT	AE1	Summary of Adverse Events During the Screening/Run-in Period	ICH E3	SAC
3.5.	ITT	AE13	Overview of On-treatment Adverse Events		SAC
3.6.	ITT	Study Specific	Overview of On-treatment Adverse Events per Thousand Person-Years		SAC
3.7.	ITT	AE1	Summary of On-Treatment Adverse Events		SAC
3.8.	ITT	Study Specific	Summary of On-Treatment Adverse Events per Thousand Person-Years		SAC
3.9.	ITT	AE1	Summary of Post-Treatment Adverse Events		SAC
3.10.	ITT	AE1	Summary of Post-Study Adverse Events		SAC
3.11.	ITT	AE1	Summary of On-Treatment Drug-Related Adverse Events	ICH E3	SAC
3.12.	ITT	Study Specific	Summary of On-treatment Drug-Related Adverse Events per Thousand Person-Years		SAC
3.13.	ITT	AE1	Summary of Post-Treatment Drug-Related Adverse Events		SAC
3.14.	ITT	AE3	Summary of Common On-Treatment Adverse Events (1% or more of Subjects in Any Treatment Group)	ICH E3	SAC

Safety: Tables					
No.	Population	IDSL / Example Shell	Title	Programming Notes	Deliverable [Priority]
3.15.	ITT	AE3	Summary of Common On-Treatment Adverse Events (3% or more of Subjects in Any Treatment Group)	ICH E3	SAC
3.16.	ITT	Study Specific	Summary of the 10 Most Frequent On-Treatment Adverse Events in Each Treatment Group		SAC
3.17.	ITT	AE1_by	Summary of On-Treatment Adverse Events by Age Group		SAC
3.18.	ITT	AE1_by	Summary of On-Treatment Adverse Events by Gender		SAC
3.19.	ITT	AE1_by	Summary of On-Treatment Adverse Events by Race		SAC
3.20.	ITT	AE1_by	Summary of On-Treatment Adverse Events by Region		SAC
3.21.	ITT	AE1_by	Summary of On-Treatment Adverse Events by Eosinophils at Screening		SAC
3.22.	ITT	AE15	Summary of On-Treatment Common ( $\geq 3\%$ ) Non-serious Adverse Events by System Organ Class and Preferred Term (Number of Subjects and Occurrences)	FDAAA, EudraCT	SAC
Serious and Other Significant Adverse Events					
3.23.	ITT	AE1	Summary of On-Treatment Serious Adverse Events		SAC
3.24.	ITT	Study Specific	Summary of On-treatment Serious Adverse Events per Thousand Person-Years		SAC
3.25.	ITT	AE1	Summary of Post-Treatment Serious Adverse Events		SAC
3.26.	ITT	AE1	Summary of Post-Study Serious Adverse Events		SAC
3.27.	ITT	AE1	Summary of On-Treatment Drug-Related Serious Adverse Events		SAC
3.28.	ITT	Study Specific	Summary of On-treatment Drug-Related Serious Adverse Events per Thousand Person-Years		SAC

Safety: Tables					
No.	Population	IDSL / Example Shell	Title	Programming Notes	Deliverable [Priority]
3.29.	ITT	AE1	Summary of On-Treatment Adverse Events Leading to Permanent Discontinuation of Study Drug or Withdrawal from Study		SAC
3.30.	ITT	AE1	Summary of Post-Treatment Adverse Events Leading to Withdrawal from Study		SAC
3.31.	ITT	AE1	Summary of On-Treatment Adverse Events of Special Interest		SAC
3.32.	ITT	Study Specific	Summary of On-Treatment Adverse Events of Special Interest per Thousand Person-Years		SAC
3.33.	ITT	AE1	Summary of Post-Treatment Adverse Events of Special Interest		SAC
3.34.	ITT	AE1	Summary of On-Treatment Serious Adverse Events of Special Interest		SAC
3.35.	ITT	Study Specific	Summary of On-Treatment Serious Adverse Events of Special Interest per Thousand Person-Years		SAC
3.36.	ITT	AE1	Summary of Post-Treatment Serious Adverse Events of Special Interest		SAC
3.37.	ITT	AE16	Summary of On-Treatment Serious Adverse Events by System Organ Class and Preferred Term (Number of Subjects and Occurrences)	FDAAA, EudraCT	SAC
MACE					
3.38.	ITT	Study Specific	Summary of On-Treatment Major Adverse Cardiac Events (MACE) – Narrow Definition		SAC
3.39.	ITT	Study Specific	Summary of On-Treatment Major Adverse Cardiac Events (MACE) Per Thousand Person-Years – Narrow Definition		SAC
3.40.	ITT	Study Specific	Summary of On-Treatment Major Adverse Cardiac Events (MACE) – Broad Definition		SAC

Safety: Tables					
No.	Population	IDSL / Example Shell	Title	Programming Notes	Deliverable [Priority]
3.41.	ITT	Study Specific	Summary of On-Treatment Major Adverse Cardiac Events (MACE) Per Thousand Person-Years – Broad Definition		SAC
Pneumonia and Radiography (Chest X-Rays)					
3.42.	ITT	Study Specific	Summary of On-Treatment Pneumonia, Including Chest X-ray Finding		SAC
ECG					
3.43.	ITT	EG2	Summary of ECG Values (On-Treatment)	IDSL	SAC
3.44.	ITT	EG2	Summary of Change from Baseline in ECG Values (On-Treatment)	IDSL	SAC
3.45.	ITT	EG1	Summary of ECG Findings (On-Treatment)	IDSL	SAC
3.46.	ITT	Study Specific	Summary of ECG Findings Shifts from Baseline (On-Treatment)		SAC
3.47.	ITT	Study Specific	Summary of ECG Abnormalities (On-Treatment)		SAC
3.48.	ITT	Study Specific	Analysis of Mean Change from Baseline in PR interval (msec) (On-Treatment)		SAC
3.49.	ITT	Study Specific	Analysis of Mean Change from Baseline in QTc(F) Interval (msec) (On-Treatment)		SAC
Vital Signs					
3.50.	ITT	VS1	Summary of Vital Signs (On-Treatment)	ICH E3	SAC
3.51.	ITT	VS1	Summary of Change from Baseline in Vital Signs (On-Treatment)	ICH E3	SAC
3.52.	ITT	Study Specific	Analysis of Mean Change from Baseline in Systolic Blood Pressure (mmHg) (On-Treatment)		SAC
3.53.	ITT	Study Specific	Analysis of Mean Change from Baseline in Diastolic Blood Pressure (mmHg) (On-Treatment)		SAC

Safety: Tables					
No.	Population	IDSL / Example Shell	Title	Programming Notes	Deliverable [Priority]
3.54.	ITT	Study Specific	Analysis of Mean Change from Baseline in Pulse Rate (beats/min) (On-Treatment)		SAC

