Treatment Assignment	
 
Eligible participants will enter a 2-week run-in period on fluticasone furoate [FF], 100 mcg daily via the ELLIPTA™ DPI.
 
At the end of the run-in period, eligible participants are to be randomized 1:1:1 to receive one of the following three double-blinded treatments: 
 
UMEC 62.5mcg
 
UMEC 31.25mcg
 
Placebo
 
 
 
The randomization code will be generated using GlaxoSmithKline (GSK) software (RAMOS NG). The study will use one central randomization schedule to allocate treatments for all randomized participants.
 
Participants will be randomized using an IWRs system (RAMOS NG).
 

Interim Analysis	
 
No interim is planned for this study.
 

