### 4. ANALYSIS POPULATIONS

Population	Definition / Criteria	Analyses Evaluated
All Subjects Enrolled	

This population will comprise all participants for whom a record exists on the study database, including pre-screened participants that sign the informed consent document but do not complete a Visit 1 (screening) procedure (i.e., pre-screening failures), or participants that complete at least one Visit 1 procedure but do not enter the run-in period (i.e., screening failures).

	

Study Population

All Subjects Screened	

This population contains all participants that complete at least one Visit 1 (Screening) procedure

	

Study Population

Safety

Randomized	

This population will comprise of all participants who were randomized (i.e. were assigned a randomization number)

	

Study population

Intent-to-Treat (ITT)	

This population will comprise all randomized participants, excluding those who were randomized in error. A participant who is recorded as a screen failure or run-in failure but is randomized and does not receive a dose of study treatment, is considered to be randomized

	

Study population

Efficacy

Safety

Population	Definition / Criteria	Analyses Evaluated
	in error. This population will be based on the treatment the participant was randomized to receive.	

Refer to [Appendix 9](#) : List of Data Displays which details the population used for each display.

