## 8. SAFETY ANALYSES

The safety analyses will be based on the ITT population including all data collected during the study. Participants will be analyzed according to the treatment they were randomized to. On-treatment safety data collected at scheduled clinic visits will be summarized and analyzed by treatment and by visit, unless otherwise specified. Run-in adverse events, on-treatment adverse events and post-treatment adverse events will be summarized separately.

**Table 5** provides an overview of the planned analyses, with further details of data displays being presented in [Appendix 9: List of Data Displays](#).

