## 8.1. Extent of Exposure

Exposure will be summarized for the ITT population.

Exposure to open label FF 100mcg during the run-in period will be summarized and presented in the following categories:  $\geq 1$  day,  $\geq 1$  week,  $\geq 2$  weeks.

Overall extent of exposure to open label FF 100mcg and to double blind study treatment during the randomized treatment period will be summarized in increments of 4 weeks for  $\geq 1$  day,  $\geq 4$  weeks,  $\geq 8$  weeks,  $\geq 12$  weeks,  $\geq 16$  weeks,  $\geq 20$  weeks,  $\geq 24$  weeks. The category 24 weeks (-5/+2 days) will also be presented to capture the number of participants completing treatment per protocol, including permitted visit windows.

Post-treatment duration in study will also be summarized using the categories 0 weeks (i.e. participants who discontinued IP and withdrew from the study at the same time),  $>0$  to 4 weeks,  $>4$  to 12 weeks and  $>12$  weeks for participants who prematurely discontinued from study treatment. The number of days of post-treatment data will also be summarized for all participants with at least one day of post-treatment data.

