### 10.9.10. ICH Listings

ICH: Listings					
No.	Population	IDSL / Example Shell	Title	Programming Notes	Deliverable [Priority]
Subject Disposition					
1.	All Subjects Screened	ES7	Listing of Reasons for Screen Failure, Run-in Failure or Randomization Failure	Journal Guidelines	SAC
2.	ITT	ES3	Listing of Reasons for Study Withdrawal	ICH E3	SAC
3.	ITT	SD3	Listing of Reasons for Study Treatment Discontinuation	ICH E3	SAC
4.	ITT	BL2	Listing of Subjects for Whom the Treatment Blind was Broken	ICH E3	SAC
5.	ITT	Study Specific	Listing of Randomized and Actual Treatments	ICH E3	SAC
6.	ITT	Study Specific	Listing of Study Treatment Misallocations	ICH E3	SAC
Protocol Deviations					
7.	All Subjects Enrolled	DV2	Listing of Important Protocol Deviations	ICH E3	SAC
8.	ITT	IE3	Listing of Subjects with Inclusion/Exclusion Criteria, or Randomization Deviations	ICH E3	SAC
Populations Analyzed					
9.	ITT	Study Specific	Listing of Subjects Excluded from the Primary Efficacy Analysis	ICH E3	SAC
10.	All Subjects Screened	Study Specific	Listing of Subjects Who Were Randomized in Error and Not Included in the Intent-To-Treat Population	ICH E3	SAC
Demographic and Baseline Characteristics					
11.	ITT	DM4	Listing of Demographic Characteristics	ICH E3	SAC
12.	ITT	DM10	Listing of Race	ICH E3	SAC

ICH: Listings					
No.	Population	IDSL / Example Shell	Title	Programming Notes	Deliverable [Priority]
Treatment Compliance					
13.	ITT	Study Specific	Listing of Treatment Compliance Data	ICH E3	SAC
Efficacy					
14.	ITT	Study Specific	Listing of Clinic Spirometry Data	ICH E3	SAC
Exposure					
15.	ITT	EX3 (modified)	Listing of Run-in Exposure, Treatment Exposure and Post-Treatment Study Duration	ICH E3	SAC
Adverse Events					
16.	All Subjects Enrolled	AE8	Listing of All Adverse Events for Subjects Not Included in the ITT Population	ICH E3	SAC
17.	ITT	AE8	Listing of All Adverse Events	ICH E3	SAC
18.	ITT	Study Specific	Listing of Adverse Events for Subjects Who Received an Incorrect Treatment	ICH E3	SAC
19.	ITT	AE7	Listing of Subject Numbers for Individual Adverse Events	ICH E3	SAC
20.	Not Applicable	AE2	Listing of Adverse Event System Organ Classes, Preferred Terms, and Verbatim Text	IDSL	SAC
Serious and Other Significant Adverse Events					
21.	ITT	AE8	Listing of Fatal Serious Adverse Events	ICH E3	SAC
22.	ITT	AE8	Listing of Non-Fatal Serious Adverse Events	ICH E3	SAC

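### Tables 3.1 and 3.4 cover run-in FF exposure and AEs in randomised participants only, so no table gives run-in AE or SAE incidence among all who took open-label FF

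*SAP*

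**What the plan says.** - **Run-in treatment.** Section 2.3: "Eligible participants will enter a 2-week run-in period on fluticasone furoate [FF], 100 mcg daily", before randomisation.
- **Safety population.** Section 8: "The safety analyses will be based on the ITT population including all data collected during the study". Section 8.1: "Exposure will be summarized for the ITT population".
- **ITT.** Section 4: "This population will comprise all randomized participants, excluding those who were randomized in error".
- **Run-in displays.** In Section 10.9.8, Table 3.1 ("Summary of Exposure to Open-Label FF100mcg During the Run-in Period") and Table 3.4 ("Summary of Adverse Events During the Screening/Run-in Period") both carry the population ITT.
- **All Subjects Screened.** Section 4: "This population contains all participants that complete at least one Visit 1 (Screening) procedure". Its stated uses are study population and safety.
- **Participants outside ITT.** Section 10.9.10, Listing 16, on All Subjects Enrolled: "Listing of All Adverse Events for Subjects Not Included in the ITT Population". Section 10.4.1 gives their events a pre-treatment phase, which is not one of the phases in that section's table.

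**The concern.** Run-in is a period of exposure to trial-supplied drug, and Table 3.4 is the only planned table of AEs in that period. By using ITT it is conditioned on having been randomised. A participant whose AE on FF prevented randomisation is in neither the numerator nor the denominator, and that participant's FF exposure is missing from Table 3.1.

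At stake is the description of what happened on open-label FF before randomisation, particularly events serious enough to end participation. A reader who takes Table 3.4 as the AE experience of everyone given run-in FF would be looking only at those who got through it, and no other table supplies the full picture. The population column in Section 4 suggests that a wider safety population was intended for something, but the display list never uses it for safety.

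**Working it through.** **Step 1: where an AE or SAE that ended run-in can appear**

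| Display (SAP section) | Population or scope | Can it hold the event? |
|---|---|---|
| Table 3.4, run-in AEs (10.9.8) | ITT | No |
| Table 3.1, run-in FF exposure (10.9.8) | ITT | Participant not counted |
| SAE tables 3.23-3.28 (10.9.8) | ITT; on-treatment, post-treatment or post-study | No |
| All other tables in 10.9.8 | ITT | No |
| Listings 21-23, fatal and non-fatal SAEs, reasons for seriousness (10.9.10) | ITT | No |
| Listing 24, AEs leading to discontinuation or withdrawal (10.9.10) | ITT | No |
| Listing 16 (10.9.10) | All Subjects Enrolled, outside ITT | Yes |
| Profiles 61-69, cardiovascular event types and all-cause deaths (10.9.11) | All Subjects Enrolled | Yes, if of a profiled type |
| Table 1.4 and Listing 1, failure reasons (10.9.4, 10.9.10) | All Subjects Enrolled; All Subjects Screened | Reason for failure only |

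The exclusion follows from the ITT definition and needs no assumption. In Appendix 9, All Subjects Screened serves only Listings 1 and 10 (failure reasons, and participants randomised in error). Neither is a safety display.

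**Step 2: what this does to the overall percentage**

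The SAP states no run-in AE percentage and no number of run-in failures, so there is no planned figure to reproduce. The following is illustration only.

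- N = 174 + 69 + 21 + 114 + 58 = 436 randomised (Section 5.4).
- p = proportion of randomised participants with a run-in AE (assumed).
- f = share of run-in entrants who fail run-in (assumed); F = N/(1 - f) - N.
- q = proportion of run-in failures with an AE (assumed).

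All-entrant proportion = (N x p + F x q)/(N + F) = (1 - f) x p + f x q.

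ITT minus all-entrant = f x (p - q).

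The sign depends only on whether q exceeds p.

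With p = 10% and f = 15%, F = 436/0.85 - 436, about 77:

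| q | All-entrant | ITT minus all-entrant |
|---|---|---|
| 0% | 0.85 x 10 + 0.15 x 0 = 8.5% | +1.5 points |
| 10% | 8.5 + 1.5 = 10.0% | 0 |
| 25% | 8.5 + 3.75 = 12.25% | -2.25 points |
| 50% | 8.5 + 7.5 = 16.0% | -6.0 points |

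Over p = 5-15%, f = 5-30% and q = 0-50%, the extremes are 0.30 x (15 - 0) = +4.5 points and 0.30 x (5 - 50) = -13.5 points.

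**The case against.** The strongest defence is that the plan is consistent on this choice. Sections 8 and 8.1 say ITT, both tables are labelled ITT, and a table of run-in AEs in the analysed cohort correctly describes that cohort. The safety objective in Section 2.2 compares UMEC with placebo, and FF is background therapy. The events are not lost from the report: Listing 16 gives all AEs for participants outside ITT, profiles 61-69 cover deaths and named cardiovascular events, and Table 1.4 summarises reasons for run-in failure. The safety entry against All Subjects Screened in Section 4 does not in itself promise a table, since that section refers the reader to Appendix 9 for the population of each display.

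All of that stands. It shows that the matter is one of presentation. It does not supply a run-in AE or SAE incidence for everyone given FF, and it leaves the Section 4 entry without any display behind it.

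A reader might go further and infer that the run-in AE percentage in Table 3.4 is biased low. The SAP does not support that. Run-in failures leave the denominator as well as the numerator, and some will leave for reasons other than an AE. Section 2.3 requires an ACQ-6 score above 0.75 at Visit 2, so a participant whose asthma is well controlled on FF also fails run-in. With p = 5%, 10-25% of entrants failing and q = 10-30%, the all-entrant figure would be 5.5% to 11.25%, but those inputs presuppose q above p. With q = 0 the same inputs give 0.90 x 5 = 4.5% and 0.75 x 5 = 3.75%, both below the tabulated 5%. Nor is Table 3.4 an exposure-adjusted rate: it uses the same shell as the ordinary AE summaries, and the per-person-year tables are all on-treatment.

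**Conclusion.** The point holds as a gap in the run-in safety summaries. AEs and SAEs that ended run-in are certain to be absent from every safety table and from the SAE listings, and the FF exposure of those participants is absent from Table 3.1. This rests on the population definitions alone. The direction and size of any difference in the overall run-in AE percentage are unknown, because the SAP gives neither the number of run-in failures nor their AE frequency. The figures above show only that either direction is possible under plausible assumptions.

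Severity is minor. The randomised comparison, the primary endpoint and on-treatment safety are unaffected, and the individual events remain traceable through Listing 16 and, where applicable, profiles 61-69.

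**What to change.** 1. Produce Tables 3.1 and 3.4 for All Subjects Screened participants who took at least one dose of run-in FF, with columns for total, randomised and run-in failure. Define the dosing flag in Section 4 or 10.6.
2. Within the run-in AE summary, add SAEs and AEs leading to run-in failure.
3. Limit the ITT sentences in Sections 8 and 8.1 to the randomised period. This also gives the safety entry for All Subjects Screened in Section 4 a display to refer to.
4. Amend the pre-treatment rule in Section 10.4.1 so that run-in events of participants outside ITT fall in the Screening/Run-in phase. Otherwise changing the population on Table 3.4 may not bring them in.

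No new data collection should be needed. The schedule in Section 10.2.1 reviews AEs from Visit 1, Listing 16 already reports these events, and Section 10.6.2 already has run-in container rules for participants who were not randomised. The cost is slightly more programming than a change of population flag (one new flag, extra columns and the phase rule) and a run-in AE percentage that may change in either direction.
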